1.2 Rationale

Great strides have been made in the development of drugs that are therapeutically beneficial in RRMS, resulting in the introduction of 10 DMAs approved by the Food and Drug Administration (FDA) for clinical use. In contrast, the treatment of SPMS remains suboptimal. The only FDA sanctioned drug for the management of progressive MS is mitoxantrone, a chemotherapeutic agent that is modestly effective and carries significant toxicities, including cardiomyopathy and leukemia. There is a dire need for novel agents that stabilize the disease course in patients with SPMS without imposing undue risks.

Although focal blood-brain-barrier breakdown and perivascular infiltrates are relatively more common in RRMS, a substantial body of data indicates that autoimmune inflammation is still relevant, and contributes to CNS tissue damage, during the SP stage. However, neuropathological studies indicate that the nature of the aberrant immune response evolves over the disease course and might explain why the efficacy of DMAs differs between the RR and SP phases. Our anecdotal experience at the UM suggests that ECP might be effective in the treatment of SPMS when administered using a more frequent and prolonged schedule than that used in previous studies. Based on this, and its favorable safety profile (both in MS and other conditions), we believe that a more rigorous evaluation of our protocol in SPMS is warranted.

2. STUDY OBJECTIVES

2.1 Primary Objective

To evaluate the effect of ECP compared to IVMP on accumulation of disability at 1 year (52 weeks) in individuals with secondary progressive multiple sclerosis (SPMS). Disability will be assessed using a composite measure that takes into account changes in the EDSS and components of the MSFC score.

2.2 Secondary Objectives

- To assess the effect of ECP versus corticosteroids on plasma levels of immunological factors and the frequency of circulating myelin-reactive Th1 and Th17 cells
- To determine whether changes in immunological parameters that occur following initiation of ECP or corticosteroids correlate with clinical outcomes
- To assess the impact of ECP versus corticosteroids on Expanded Disability Status Scale (EDSS) scores every 3 months through 2 years compared to baseline
- To assess the impact of ECP versus corticosteroids on MSFC three dimensional composite z-score every 3 months through 2 years compared to baseline
- To assess the effect of ECP on risk of clinical relapse
- To assess the effect of ECP versus corticosteroids on the frequency of gadolinium-enhancing T1 weighted lesions on cranial MRI scans obtained at months 6 and 12 compared to baseline
- To assess the effect of ECP versus corticosteroids on interval changes in T2 weighted lesion number and volume at months 6 and 12 compared to baseline.
- To assess the tolerability and the safety profiles of ECP versus corticosteroids

3. OVERALL DESIGN AND PLAN OF THE STUDY

3.1 Overview

This is a Phase II randomized, open-label study to evaluate the efficacy of extracorporeal photopheresis (ECP) versus IVMP on disability progression in subjects with SPMS. At the initial screening visit, an extensive medical history will be obtained and a detailed neurological examination will be performed to determine eligibility. Subjects who meet eligibility criteria will be enrolled in one of two study arms. Subjects will be randomized at a 1:1 ratio to receive ECP (study arm) or active treatment with intravenous methylprednisolone pulses (control arm) administered every 4 Weeks (1 gram per infusion) for 52 weeks.

ECP will be administered according to the following schedule:

Study Arm: Weeks 1-8: 3 times per week

Weeks 9-16: Twice per week

Weeks 17-36: Treatment on two consecutive days every 2 weeks (or optionally, one treatment per week)

Weeks 37-43: Once every 2 weeks

Weeks 44-52: Once every 4 Weeks

[figure not shown]
All subjects, including patients who receive corticosteroids, will be evaluated using the MSFC tool at baseline and every 3 months through 2 years (See Section 9.1 for timing of the schedule of assessments). They will also be scored using the EDSS at baseline and every 3 months through 2 years. Subjects in the control arm will be evaluated by MSFC and EDSS during the week prior to their next intravenous methylprednisolone infusion. Blood will be collected for immune function (cytokines) testing at baseline, and months 3, 6, 9 and 12. MRI will be done at baseline as well as months 6 and 12 following initiation of treatment; if the disability measurements are stable or improved at any point in time, then ECP will be continued per protocol..

Patients in the ECP arm should have all of their treatments with the CELLEX[®] System. Patients randomized to the ECP arm must receive their treatment within 5 days of baseline visit.

In the ECP process, UVADEX[®] (methoxsalen) Sterile Solution will be injected directly the recirculation bag of the extracorporeal circuit after completion of the buffy coat collection. The dose of UVADEX[®] (methoxsalen) Sterile Solution will be calculated based on the standard treatment volume formula (See Section 6.2).

For the schedule of assessments, please refer to Section 0.

Figure 1: Study Design

ECP=Extracorporeal Photopheresis MRI: Magnetic Resonance Imaging

¹ Frequency of ECP treatments:

Three times weekly for weeks 1-8, followed by a taper to twice weekly for weeks 9-16 and then twice consecutively every 2 weeks (or alternatively once weekly) for weeks 17-36, then once every 2 weeks for weeks 37-43, and once every 4 weeks for weeks 44-52.

² Pulsed corticosteroids, IVMP (1 g IV methylprednisolone) every 4 Weeks for 52 Weeks.

³ EDSS and MSFC will be assessed every 3 months through 2 years

3.2 Endpoints

3.2.1 Primary Endpoint

Proportion of subjects with no evidence of disease progression at week 52. Progression is defined as a minimum change from baseline in one or more of the following parameters:

- 20% or greater increase in the timed 25 foot walk
- 20% or greater increase in the 9 hole peg test
- 1 point or greater increase in EDSS score in subjects with baseline EDSS scores between 3 and 5.5
- 0.5 point or greater increase in EDSS score in subjects with baseline EDSS scores equal to or greater than 6

3.2.2 Secondary Endpoints

- Change in Plasma levels of Immunological Factors and Frequencies of IFN γ and IL-17 MBP-specific PBMC at Months 3, 6, 9 and 12 compared with baseline
- MSFC 3 dimensional composite z-score every 3 months through 2 years compared to baseline
- EDSS score every 3 months through 2 years compared to baseline
- Percentage of subjects with improvement (as defined for the primary endpoint) at Months 3, 6, 9 and 12 compared to baseline
- Occurrence of clinical relapse at any point in the study
- Interval change in T2 lesion number and volume on MRI scans obtained at months 6 and 12 compared to baseline
- The number and volume of gadolinium enhancing lesions on MRI scans obtained at months 6 and 12 compared to baseline
- Interval change in the number and volume of gadolinium enhancing lesions on MRI scans obtained at months 6 and 12 compared to baseline.
- Toxicity and Adverse events in both arms

3.3 Justification of the Study Design

Mitoxantrone is the only therapy FDA-approved for the treatment of SPMS in the United States. However, the efficacy of mitoxantrone in SPMS patients without superimposed relapses is unknown and the considerably toxicities associated with this chemotherapy (including nausea, alopecia, menstrual disorders, urinary tract infections, amenorrhea and SAEs such as secondary acute myelogenous leukemia, hepatotoxicity and cardiomyopathy) limit its use.

In contrast, ECP has an excellent safety and toxicity profile, even in patients using it long term. Experience with a similar dosing schedule has shown an excellent safety profile. In a Phase 2 randomized study of ECP versus no ECP in chronic GVHD, Flowers et al treated 48 patients with ECP three times weekly on week 1, and then twice weekly from weeks 2 through 12. Treatments were tapered thereafter according to response, and there was no difference in the incidence of adverse events between patients receiving ECP (n=48) and the control arm (n=47). Infections, particularly pneumonia, were the main adverse event, likely related to chronic GVHD itself. Couriel et al treated 71 patients with 2-4 treatments per week, with taper according to response. Only 4 patients developed toxicity that was mild, reversible and did not require discontinuation of therapy. These events included: abdominal pain, variations in blood pressure and fever. Jagasia et al, and Greinix et al used similar treatment schedules in 64 and 59 patients respectively, with no reported toxicities. Abreu et al treated 28 patients with Crohn's Disease twice weekly for the first 4 weeks, and then twice weekly every other week for 24 weeks. Only 2 patients required discontinuation for adverse events attributed to ECP, including nausea, malaise and fever with an increase in CRP. Again, these adverse events are difficult to separate from the manifestations of the disease, and the authors conclude that the treatment was well tolerated. In a UK Consensus Statement on the use of ECP in GVHD (Scarlsbrick et al), the expert panel reported separately on schedules for GVHD and those used for CTCL. The reason for this was that the "accelerated" regimen was reported to gain rapid control of GVHD with 2 to 3 consecutive treatments every 1 to 3 weeks. Considering MS is an autoimmune disorder, we opted for the schedules more commonly used in other autoimmune diseases like chronic GVHD or Crohn's Disease.

If ECP is proven to be therapeutically efficacious in SPMS, it will revolutionize the treatment of that disorder. Intravenous methylprednisolone pulses will be used in the comparator arm. Pulse corticosteroids are commonly used as an adjunctive therapy or monotherapy to manage symptoms in SPMS ([Zephir H et al. 2005](#)) A randomized, controlled, single blind phase II clinical trial of regular pulses of intravenous methylprednisolone administered to MS patients over 5 years showed beneficial effects including prevention or delay of whole brain atrophy and disability progression, and suppression of T1-weighted MRI lesion formation (Zivodinov, et al. 2001). Furthermore, prolonged treatment with pulsed intravenous methylprednisolone was safe and well tolerated. Additionally, with the current design, patients who did receive mitoxantrone prior to accrual will still be able to participate in this study, unless they received treatment with it in the last two years.

Patients must be at least 18 years of age and must be able to provide informed consent.

4. STUDY POPULATION

The study population will consist of patients with SPMS. Patients must be able to provide written consent and meet all the inclusion criteria and none of the exclusion criteria.

4.1 Inclusion Criteria

1. Patients with SPMS based on the Recommended Diagnostic Criteria for MS and clinical course. Secondary progression is defined by a progressive increase in disability (of at least 6 months duration) in the absence of relapses or independent of relapses.
2. Demonstrate EDSS scores between 3 to 6.5 at screening.
3. Documented EDSS progression in the 2 years prior to screening of 1 point or greater for patients with an EDSS score less than 6 at baseline, and greater than or equal to 0.5 for patients with an EDSS score greater than or equal to 6.0 at baseline. If documented EDSS scores are not available, a written summary of the clinical evidence of disability progression over the last 2 years, and retrospective assessment of EDSS score from data in the medical records, must be submitted for review by the principal investigators.
4. Documented absence of clinical relapse within 2 years of screening
5. Age $\geq 18 \leq 75$ years
6. Weight $> 40 \leq 150$ kg.
7. Absolute Neutrophil count $\geq 2,000$ per μL
8. Hematocrit $\geq 28\%$ and platelet count $> 100,000$ per μL (with or without transfusion support)
9. Willingness to use at least 1 reliable method of birth control (e.g. abstinence, oral contraceptives, intrauterine devices, barrier method with spermicide, or surgical sterilization) throughout the study for all men and women of childbearing potential
10. Willingness to participate in all study visits and procedures, as outlined in the informed consent
11. Patients able to give informed consent.
12. Patients must have adequate peripheral venous access to initiate ECP therapy.

4.2 Exclusion Criteria

1. Absolute medical contraindication to corticosteroid treatment
2. Absolute medical contraindication to receive ECP
3. Clinical relapse within 2 years of screening
4. Laboratory evidence of any of the following:
 - a. WBC $< 2,000$ cells per uL
 - b. Serum transaminase levels $> x 2$ UNL
 - c. Creatinine Clearance < 60 mL/min
 - d. HgbA1C $> 6\%$

5. Concurrent diagnosis of a neurological condition that would interfere with the assessment of MS, or an autoimmune disease or inflammatory condition that is chronically treated with immunosuppressive agents, including systemic corticosteroids.
6. Evidence of known infection with human immunodeficiency virus (HIV) or active (not including latent) Hepatitis B (laboratory testing is not required if virus status is already known)
7. Uncontrolled infection requiring treatment at study entry
8. Hypersensitivity or allergy to psoralen (methoxalen)
9. Hypersensitivity or allergy to both heparin and citrate products (If hypersensitive or allergic to only one of these products, exclusion does not apply)
10. Inability to tolerate fluid changes associated with ECP (e.g. inadequate renal, hepatic, pulmonary and cardiac function leading to enable patient to tolerate extracorporeal volume shifts associated with ECP)
11. Presence of aphakia or photosensitive disease (systemic lupus erythematosus, porphyrias, albinism, etc.)
12. Women who are pregnant and/or lactating.
13. Use of any investigational drug/treatment at the time of enrollment or within the previous 60 days, or five elimination half-lives, or until the expected pharmacodynamic effect has returned to baseline, whichever is longer.
14. Initiation of dalfampridine or change in the dose of dalfampridine within 6 months prior to randomization
15. Treatment with any of the medications or procedures listed below:
 - Glatiramer acetate, interferon-beta, fingolimod, teriflunomide or dimethylfumarate within 3 months prior to randomization
 - Natalizumab within 3 months prior to randomization
 - Cyclophosphamide within 1 year prior to randomization
 - Mitoxantrone within 1 years prior to randomization
 - Rituximab within 6 months prior to randomization
 - Ofatumumab, ocrelizumab, cladribine, daclizumab within 2 years prior to randomization
 - Intravenous immunoglobulin within 6 months prior to randomization
 - Plasmapheresis within 6 months prior to randomization
16. Corticosteroids within 3 months prior to screening, with the following exceptions: Topical ointments or creams, or eye drops that contain corticosteroids; Intranasal Steroids or Oral Steroids given in a single dose as a premedication for a procedure such as gadolinium-enhanced MRI.
17. Inability to undergo MRI scans
18. Contraindication to gadolinium due to past allergic, hypersensitive or adverse reaction or impaired renal function. Patients receiving a steroid prep prior to Gadolinium administration due to history of hypersensitivity or allergy to other agents or due to prior mild reaction to Gadolinium will not be excluded from the study. Any other disease or

condition which, in the opinion of the investigator, could interfere with participation in the study according to the study protocol, or with the ability of the patients to cooperate and comply with study procedures.

19. Poor venous access
20. Previous history of skin cancer, leukemia/lymphoma/myeloma or bone marrow transplant.
21. Patients taking Coumadin who are unable to switch from oral anticoagulants to enoxaparin.
22. Heparin-induced thrombocytopenia
23. Poor cardiac function
24. Severe hypotension

5. PATIENT WITHDRAWAL AND REPLACEMENT

Patients may withdraw from the study at any time without penalty and for any reason without prejudice to his or her future medical care.

Patients must be withdrawn under the following circumstances:

- The patient withdraws consent
- Pregnancy (see Section 8.2.2.9)
- Unacceptable toxicity including patients on corticosteroids who develop psychosis or aseptic necrosis of the femoral head

Patients may be required to withdraw after discussion with the investigator for the following reasons:

- AE(s)
- At the discretion of the investigator
- Violation of eligibility criteria
- Deviation from the treatment plan specified in the protocol (e.g., incorrect administration of the study drug, failure to attend study visits, etc.)
- The treating physician can withdraw the patient from the study at any time and for any medical reason that he/she deems necessary
- The patient has a right to withdraw at any time, for any medical or other reasons.
- Patients who experience a clinical relapse (defined as neurological event characterized by new or worsening symptoms lasting 48 hours after a stable period of at least 30 days and is considered in the judgment of the investigator to be a clinical relapse). Patients who fail therapy will be off study, and further therapy will be at the discretion of the treating neurologist. The study will not cover any form of therapy after the patient is off study.
- Patients who have interval accumulation of T1 or T2 lesions and/ or gadolinium enhancing T1 lesions on the month 6 MRI scan
- In all cases, the reason(s) for withdrawal, and the primary reason, must be recorded on the case report form (CRF) or similar.

Withdrawn patients will be replaced.

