Dosage and frequency of administration	Study Arm: Weeks 1-8: 3 times per week Weeks 9-16: Twice per week Weeks 17-36: Treatment on two consecutive days every 2 weeks (or optionally, one treatment per week) Weeks 37-44: Once every 2 weeks Weeks 45-52: Once every 4 Weeks Control Arm: Pulsed corticosteroids (1 gm. of MP IV every month) for 52 Weeks.
Duration of Administration	1 year (52 weeks)
Statistical methods	An intent to treat approach will be used. The proportion of subjects who show no evidence of disease progression, as defined above, will be compared between treatment groups using the Chi-square test. Two-sample t-tests or Wilcoxon rank sum tests will be used to assess treatment differences in continuous outcomes and chi-square or Fisher's exact tests will be used for categorical outcomes.
Power and Sample Size	Assuming that the proportion of subjects in the corticosteroid treatment who show no evidence of disease progression at Week 52 is 30%, 66 subjects (33 per treatment arm) provides at least 80% power to detect a treatment difference of 30% (i.e., 60% of the ECP treated subjects will improve at Week 17), based on the normal approximation of the binomial distribution and a one-sided Type I error of 5%.

LIST OF STUDY PERSONNEL

Sponsors	[name]. Director Adult BMT Program and ECP. University of Michigan
Principal Investigator	[name]. Director Adult BMT Program and ECP. University of Michigan [contact]. [contact]
Co-Principal Investigator	[name]. Holtom-Garrett Family Professor of Neurology and Director of Multiple Sclerosis Center, University of Michigan [contact] [contact]
SAE/Adverse Event Reporting	[name] [contact]
Laboratory	University of Michigan Clinical Laboratories for routine studies Neuroimmunology Laboratory, Dept. of Neurology for research studies ([name], Director)

TABLE OF CONTENTS

PROTOCOL SYNOPSIS	4
LIST OF STUDY PERSONNEL	11
TABLE OF CONTENTS	12
LIST OF ABBREVIATIONS AND DEFINITIONS OF TERMS	16
1 INTRODUCTION	18
1.1 Background	18
1.2 Rationale	20
2 STUDY OBJECTIVES	21
2.1 Primary Objective	21
2.2 Secondary Objectives	21
3 OVERALL DESIGN AND PLAN OF THE STUDY	22
3.1 Overview	22
3.2 Endpoints	24
3.2.1 Primary Endpoint	24
3.2.2 Secondary Endpoints	24
3.3 Justification of the Study Design	26
4 STUDY POPULATION	26
4.1 Inclusion Criteria	26
4.2 Exclusion Criteria	27
5 PATIENT WITHDRAWAL AND REPLACEMENT	28
6 TREATMENT	31
6.1 Control Arm: Corticosteroid Treatment	31
6.2 Study Arm: Extracorporeal Photopheresis	31
7 STUDY PRODUCT	31

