10.2 Efficacy Analyses

10.2.1 Analysis of Primary Endpoint

The primary end point is the proportion of subjects with no evidence of disease progression, as defined below, at Week 52. Intent to treat approach will be used. Progression is defined as a minimum change from baseline in one or more of the following parameters:

- 20% or greater increase in the timed 25 foot walk
- 20% or greater increase in the 9 hole peg test
- 1 point or greater increase in EDSS score in subjects with baseline EDSS scores between 3 and 5.5
- 0.5 point or greater increase in EDSS score in subjects with baseline EDSS scores equal to or greater than 6

The proportion of subjects who have not progressed clinically, based on the above criteria, at Week 52 after initiation of study therapy will be compared between treatment groups using the Chi-square test.

The early drop-outs, including patients who withdraw will be considered as non-responders.

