10.2.2 Analysis of Secondary Endpoints

The secondary endpoints include:

- Change in Plasma levels of Immunological Factors and Frequencies of IFN γ and IL-17 MBP-specific PBMC at months 3, 6, 9 and 12 compared with baseline
- MSFC 3 dimensional composite z-score at every 3 month time point through 2 years compared to baseline
- Expanded Disability Status Scale (EDSS) score at every 3 month time point through 2 years compared to baseline
- Percentage of subjects with improvement (as defined for the primary endpoint) at months 3, 6, 9 and 12 compared to baseline
- Occurrence of clinical relapse at any point in the study

- Interval change in T2 lesion number and volume on MRI scans obtained at months 6 and 12 compared to baseline
- The number and volume of gadolinium enhancing lesions on MRI scans obtained at months 6 and 12 compared to baseline
- Interval change in the number and volume of gadolinium enhancing lesions on MRI scans obtained at months 6 and 12 compared to baseline.
- Toxicity and Adverse events in both arms

For continuous outcomes, two-sample t-tests or Wilcoxon rank sum tests will be used to compare the treatment arms. For categorical outcomes, Chi-square tests or Fisher's exact test will be used to compare the treatment arms. The proportion of subjects who experience adverse events and serious adverse events will be summarized by treatment group descriptively; no inferential tests will be performed.

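### Month 6 lesion activity, relapse and failed therapy can take patients off study, and section 10.2.2 does not say how leavers enter the later MRI, EDSS and MSFC comparisons, which risks outcome-dependent selection.

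*Combined protocol and SAP*

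**What the plan says.** Section 5 separates mandatory from discretionary withdrawal. The discretionary list opens with "Patients may be required to withdraw after discussion with the investigator for the following reasons" and includes "Patients who have interval accumulation of T1 or T2 lesions and/ or gadolinium enhancing T1 lesions on the month 6 MRI scan". Clinical relapse is on the same list, and the relapse item adds that patients who fail therapy go off study, without defining failure. The section ends: "Withdrawn patients will be replaced".

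Section 10.2.2 names as secondary endpoints "Interval change in T2 lesion number and volume on MRI scans obtained at months 6 and 12 compared to baseline" and "Interval change in the number and volume of gadolinium enhancing lesions on MRI scans obtained at months 6 and 12 compared to baseline", together with EDSS and the MSFC z-score every 3 months through 2 years. The method is one sentence: "For continuous outcomes, two-sample t-tests or Wilcoxon rank sum tests will be used to compare the treatment arms". It gives no analysis set, no missing-data rule, and nothing on leavers or their replacements.

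Three other places bear on the point:
- Section 10.2.1, under the primary endpoint: "The early drop-outs, including patients who withdraw will be considered as non-responders". This suits a yes/no outcome; it assigns no lesion count, volume or z-score.
- Synopsis, statistical methods: "An intent to treat approach will be used". No imputation rule follows.
- Section 9.2.8: anyone withdrawing before Week 52 must have the Week 52 assessments at that time. Section 9.2.7 shows that these include EDSS, MSFC and gadolinium MRI.

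**The concern.** An earlier value of an outcome can decide who is present for a later comparison of the same outcome. A patient with new lesions at month 6 may be taken off study before month 12. If one treatment suppresses lesions, fewer of its patients meet the rule, so more poor outcomes leave the other arm. The groups left at month 12 are then no longer the randomised groups, and both look more stable than they were. Relapse and failed therapy act in the same way on later EDSS and MSFC values.

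The trial is open-label and the decision follows discussion with the investigator, so the same scan could lead to withdrawal more often in one arm. Replacement restores the head count but not the comparison: a replacement is a new patient, not the missing outcome of the one who left.

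**Working it through.** **The plan's own figures.** The only design calculation (section 10.4: 30% v 60%, 33 per arm, one-sided 5%) concerns the primary endpoint. It reproduces at 80.1% power with the pooled normal approximation and has no bearing here. The documents give no lesion rate, lesion SD, drop-out rate or MRI power.

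**Timing.** Section 9.1 sets month 6 at Week 24 ± 2 weeks and month 12 at Week 52 ± 1 month, so the month 12 window opens at about Week 48. An early-termination MRI prompted by the month 6 scan falls many weeks before that. Section 10.2.2 leaves two readings: the scan is not a month 12 value, or it is used as one.

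**Assumptions (illustration only).** Each patient has a lesion rate per 6 months from a gamma distribution with mean m and shape k. New lesions in months 0-6 and 6-12 are independent Poisson counts given that rate. Control m is 0.5 or 1.0, ECP m is half of that, and k is 0.5 or 1. A patient with any new lesion at month 6 leaves with probability 1 (all leave) or 0.5 (half leave), equally in both arms.

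**Formulas.**
- Probability of a clean month 6 scan: P0 = (1 + m/k)^(-k).
- Mean new lesions in months 6-12 given a clean month 6 scan: μ0 = m/(1 + m/k).
- True mean, baseline to month 12: 2m.
- Mean among those still scanned: μ0 if all leave; (2m + P0·μ0)/(1 + P0) if half leave.
- Mean with the early-termination (ET) scan used as month 12: m + P0·μ0 if all leave; 1.5m + 0.5·P0·μ0 if half leave.

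**Worked case, control m = 1, k = 1.** Control: P0 = 0.500, μ0 = 0.500. ECP (m = 0.5): P0 = 0.667, μ0 = 0.333. The true difference is 2.0 - 1.0 = 1.0.
- All leave: 0.500 - 0.333 = 0.167, or 17%.
- Half leave: (2 + 0.25)/1.5 - (1 + 0.222)/1.667 = 1.500 - 0.733 = 0.767, or 77%.
- ET scan as month 12, all leave: 1.250 - 0.722 = 0.528, or 53%.

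**Observed difference as a share of the true difference:**

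| Control m, k | P0 control / ECP | Still scanned, all leave | Still scanned, half leave | ET as month 12, all leave | ET as month 12, half leave |
|---|---|---|---|---|---|
| 0.5, 0.5 | 0.707 / 0.816 | 17% | 68% | 58% | 79% |
| 0.5, 1 | 0.667 / 0.800 | 27% | 73% | 62% | 81% |
| 1.0, 0.5 | 0.577 / 0.707 | 8% | 70% | 52% | 76% |
| 1.0, 1 | 0.500 / 0.667 | 17% | 77% | 53% | 76% |

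If all leave, 1 - P0 gives the share lost: 29-50% of controls and 18-33% of ECP patients.

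**Power, by simulation.** With a 60% reduction, m = 1, k = 1 and 33 per arm, a two-sided 5% Wilcoxon test on the cumulative count has about 65% power with complete data, about 43% if half leave and about 13% if all leave.

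**The case against.** A reader might infer that the plan has no provision for leavers and that a leaver contributes nothing after withdrawal. The documents do not support that: sections 9.2.8 and 9.2.7 require EDSS, MSFC and MRI at withdrawal, and the synopsis states intent to treat. What is missing is an analysis rule for those data, and for the MRI neither available reading recovers the full difference.

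A reader might also infer that the month 12 comparison will consist only of patients with clean month 6 scans. That goes too far as well. Withdrawal for MRI activity is discretionary, and section 7.5 permits systemic steroids for emerging enhancing lesions, which implies that some lesion-positive patients stay. The all-leave column is an extreme case. The risk of selection stands; its certainty does not. Steroids given to those who stay could also alter their month 12 scan, a further matter the analysis does not address.

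Third, it is tempting to say that most of the power is lost. That holds only if every lesion-positive patient leaves; with half leaving, about a third goes. With a 50% rather than 60% reduction (control means 0.3 to 1.0), complete-data power is itself only about 20-46%, so there may be little to lose.

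Finally, these are secondary endpoints in a Phase II trial, the primary endpoint has its own drop-out rule, and month 6 MRI is already a listed endpoint. That limits the weight of the point but does not remove it.

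**Conclusion.** The concern holds as a risk created by an unstated analysis rule. An outcome-dependent, discretionary reason for leaving precedes later comparisons of the same or related outcomes, and section 10.2.2 says nothing about leavers, early-termination scans or replaced patients.

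Under the assumed lesion model, the month 12 difference among those still scanned falls to 8-27% of its true value if all lesion-positive patients leave, and to roughly 70-75% (68-77% over the grid) if half do. Using the early-termination scan as month 12 gives 52-62% and 76-81%. The shrinkage toward no difference assumes that discretion is used equally in both arms; unequal use could push the result either way. The true size cannot be found from the documents. Lesion volumes, gadolinium endpoints, EDSS and MSFC were not modelled, so for those the argument is about direction only.

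This should be changed before analysis, but it does not threaten the primary endpoint.

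**What to change.** In section 10.2.2:

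1. Name month 6 as the main time point for the MRI endpoints. That scan precedes the MRI rule, although patients who left earlier for other reasons will still be missing.
2. Analyse EDSS and MSFC change with a repeated-measures model in all randomised patients, using every visit before withdrawal, in place of separate two-sample tests in those still attending.
3. Label month 12 MRI supportive. Define its set as all randomised patients, including those later replaced. State that an early-termination scan near month 6 is not an ordinary month 12 scan. Use carried-forward counts and worst-rank scoring as sensitivity analyses only. Worst-rank scoring is unsuitable as the main analysis because a discretionary open-label decision would set the outcome: a withdrawn patient with one new lesion would rank below a retained patient with five.

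The sponsor should also reconcile sections 5, 7.5 and 9.2.8, so that it is clear who leaves, who stays and which scans result. No clinical rule is proposed here.

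The cost is SAP wording and modest programming, using visits already scheduled and the withdrawal reason that section 5 already requires on the CRF. The downsides are that month 12 MRI loses prominence and that the model assumes withdrawal depends on observed data.
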